This conviction stems from our extensive preclinical study that demonstrated pleiotropic beneficial effects of PPIs in regulating tissue inflammation and fibrosis induced by chemotherapy or ionizing radiation. Our most recent data in a mouse model of RD shows that PPIs have remarkable effect in protecting the skin from the harmful effects of ionizing radiation. Primarily, we aim to evaluate the safety and tolerability of Dermaprazole cream in HNC patients at risk of developing RD. This study will consist of 2 arms: arm 1 consists of 30 HNC patients who will be using Dermaprazole twice daily while arm 2 consists of 15 HNC patients using Aquaphor, the current clinical standard of care.

We will assess for treatment-related adverse effects including burning, itching, tenderness, rash, and any other local or systemic allergic reactions. In addition, we will collect patient- reported quality of life questionnaire (skindex16) throughout the treatment period and during the follow up period. Furthermore, inflammatory markers including CRP, TNFa, IL-1b, and IL-6 will be drawn, pre-treatment, in the last week of treatment, and post-treatment. If found safe and effective, our product has the potential to dramatically impact clinical practice by significantly decreasing treatment-related morbidity and allowing adherence to the prescribed dose of RT which may otherwise be interrupted because of severe dermatitis.

We will track the dose delivered to the skin in the treatment planning system and repeat a simulation in the last week of therapy to assess the accuracy of this tracking and possible RD correlation with updated dosimetry from the new scan.

STUDY SCHEMA

Page 3 of 23

2 OBJECTIVES

2.1 Safety/Efficacy

2.1.1 Primary Objective

A. Determine if objectively lower rates of significant radiation dermatitis occur with Dermaprazole for HNC patients receiving radiation when compared to patients receiving Aquaphor. An objective measure will be tabulated: the rate of clinically significant (CTCAE version 5 grade 2 or higher) radiation dermatitis. This measure will be reported weekly during treatment by both the treating radiation oncologist and blinded review by a board-certified dermatologist via medical photography.

2.1.2 Secondary Objectives

2.2.2.1

To assess the highest grade of CTCAE version 5 radiation dermatitis during radiation treatment

2.2.2.2

To assess the time to occurrence of CTCAE version 5 grade 2 or higher acute radiation dermatitis.

2.2.2.3

To assess the time to healing if CTCAE version 5 grade 2 or higher acute radiation dermatitis develops.

2.2.2.4

To evaluate quality of life via acute and long-term symptoms and symptom scores utilizing the SkinDex16 scoring system.

2.2.2.5

To evaluate the threshold dose at which RD appears in either arm, utilizing skin dose tracking structures (V20 to V80 in 5 Gy increments reaching skin shell contours of "skin minus 3 millimeters" and "skin minus 5 millimeters")

2.2.2.6

To evaluate the threshold dose at which RD appears in either arm, using the same metrics as in 2.2.2.5, but with a new simulation scan in the last week of radiotherapy

2.2.2.7

To evaluate the effect of dermaprazole on inflammatory markers: CRP, TNFa, IL-1b, IL-6, by measuring values before, during, and after treatment. We expect this to give further evidence for the mechanism of action of dermaprazole.

Page 4 of 23

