8 STATISTICAL CONSIDERATIONS

8.1. Study Design/Endpoints

This portion of the study is designed to evaluate toxicity profile and preliminary efficacy of prophylactic Dermaprazole cream for radiation dermatitis in head and neck cancer patients receiving chemoradiation.

The first primary outcome is rates of clinically significant radiation dermatitis as defined as NCI CTCAE version 5 grade 2 or higher. Although not expected, if half our expected enrollment in the Dermaprazole group, 50% or more of patients experience moderate intervention-related toxicity, this treatment regimen will not be considered safe. The trial will be monitored for SAEs and stopped early for safety if two treatment-related grade 3 SAEs are reported or if one treatment-related grade 4-5 SAE is reported at any point of the trial for the Dermaprazole group.

Another primary endpoint will be feasibility, which is defined as the consideration of whether the protocol implementation will be successful in terms of accrual within the expected timeframe, as well as whether patients would comply with the study protocol and necessary data collection is logistically feasible in the clinical setting. To evaluate feasibility, we will measure:

Page 14 of 23

- Accrual rate and summary of causes for non-enrollment
- Percentage of patients compliant with therapy, defined as receiving at least 60Gy to the head and neck while using prophylactic Dermaprazole as directed
- Compliance rate and rate of completion of SkinDex16 forms

All endpoints will be evaluated when the last patient completes their 3 Month follow-up visit, although patients will continue with additional regular follow-up visits as described in the protocol schedule. Since by that point a patient would have completed all treatments, the data would provide accurate estimate of compliance and acute toxicity.

For the study to be considered feasible, all of the following must be true:

- No more than 5 patients fail to complete the treatment regimen due to study drug toxicity
- No more than 15 patients fail to comply to prophylactic Dermaprazole cream application of at least 80%
- Enrollment takes no longer than 24 months, and
- Proportions of analyzable questionnaires at baseline, while on-treatment, and offtreatment during follow-up, and within questionnaires completion rates are no worse than 80%, 80%, and 60% respectively.

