8.2 Sample Size/Accrual Rate

Participants will continue to be enrolled and monitored for toxicity per the above criteria until 30 patients in arm 1 and 15 patients in arm 2 have completed the course of head and neck radiation as evaluable patients. Patients will be randomized by computer in a 2:1 fashion. Per our current database, the clinic is treating approximately 60 eligible patients per year. As such, accrual should take no longer than 12 months but will be allowed to extend to up to 24 months without closing the study.

Initial sample size for this pilot study was estimated as if this study was conducted as a phase II study. Sample size calculation was determined using significance/alpha (α) of 0.05, to at least detect a difference in incidence of 45% and power (β) of 80%. In general, rates of clinically bothersome grade II dermatitis in the literature appear to be approximately 65%. Based on our preclinical study with animal and human skin models, we expect 20% of the Dermaprazole arm to have CTCAE grade II or higher RD. Given these values, we calculated our final sample size to be approximately 39 and we aim to enroll 45 subjects.

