8.3 Analysis of Primary and Secondary Endpoints

Descriptive and summary statistics will be computed for demographic and clinical data of all subjects enrolled in the study to describe the study sample.

Toxicity will be reported as the frequency of each adverse event according to the CTCAE version 5.0 as well as the grade of each recorded adverse event (38). Generally, adverse events in this system are graded from 1 to 5, with 1 corresponding to either mild or asymptomatic clinical manifestations of toxicity and 5 corresponding to death related to the

Page 15 of 23

adverse event (see Appendix 2). Clinically relevant toxicity will be defined as grade 2 or higher, while severe toxicity will be defined as grade 3 or higher. Acute toxicity will be defined as adverse events that occur during or within 90 days after completing radiation therapy. We will consider this intervention safe if there is a grade 1 toxicity rate of <50%, a grade 2 or higher toxicity rate of <10% and no grade 3 or higher events.

Percentages of patients enrolled per month will be recorded. If the enrollment time exceeds 24 months, the study will be considered not feasible as written. Percentage of patients not enrolled will be summarized by cause.

Quality of life will be measured with the use of SkinDex16 questionnaires filled out by the patient at baseline, throughout treatment, at the completion of radiation treatment, and at each follow up visit subsequently. We will also consider the compliance to questionnaire completion and within questionnaires completion rates. This will be reported as the average proportion of questions within each form completed properly, without errors. As long as the rates are not below the minimum threshold defined above, the study will be considered feasible.

All analyses outside of the primary endpoint will be considered exploratory in nature. Chi square and t-test will be used to evaluate differences in categorical and numerical values between arms. Subgroup analyses for BMI, total dose, and comorbidity will be conducted. We will also evaluate the incidence of RD for specific radiation skin dose stratification by reviewing the V20 to V80 in 5 Gy increments reaching a skin shell representing the thickness between the skin and the "skin minus 3 millimeters" and the "skin minus 5 millimeters." This will be done on both the original dosimetry as well as a recalculated plan from the resimulation scan.

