We will also evaluate any statistically significant differences in both the absolute numbers and relative changes of the lab values: CRP, TNFa, IL-1b, IL-6 at each of the 3 time points in which they are drawn for each arm.

All statistical tests will be two-sided. We will report comparative data in good faith and emphasize that the primary intention of this study is to understand the safety and tolerability profile of Dermaprazole.

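### Time to healing is compared only among patients who reach grade 2+ dermatitis, a group the cream itself is expected to change, so the comparison cannot show an effect on healing in either direction

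*Combined protocol and SAP*

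**What the plan says.** Section 2.1.2, item 2.2.2.3, sets the objective: "To assess the time to healing if CTCAE version 5 grade 2 or higher acute radiation dermatitis develops". The condition is the event that defines efficacy. Section 8.1 states: "The first primary outcome is rates of clinically significant radiation dermatitis as defined as NCI CTCAE version 5 grade 2 or higher".

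Section 8.2 plans for a large difference in that event. For the control rate, "rates of clinically bothersome grade II dermatitis in the literature appear to be approximately 65" (per cent); for the cream, "we expect 20% of the Dermaprazole arm to have CTCAE grade II or higher RD".

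Section 8.3 has no analysis written for time to healing. Its only between-arm method is general: "Chi square and t-test will be used to evaluate differences in categorical and numerical values between arms". It adds: "All statistical tests will be two-sided". It also labels everything outside the primary endpoint as exploratory.

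The documents do not define healing, give no value to patients who never reach grade 2, and have no rule for patients not yet healed. Section 8.4 limits the analysis to patients who complete at least 60 Gy and attend 30-day follow-up.

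**The concern.** Randomisation makes the arms comparable as whole groups. It does not make the patients with grade 2+ dermatitis on one arm comparable with those on the other when treatment changes who gets it. If the plan's rates hold, the healing comparison sets the 20% of Dermaprazole patients who reacted despite the cream against the 65% of Aquaphor patients who reacted without it.

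This matters if what drives occurrence also drives duration, and section 3.1 makes that plausible. It names obesity and diabetes as risk factors for radiation dermatitis, and lists body mass index and diabetes among the predictors of prolonged effect.

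The problem is separate from censoring and would remain if every healing date were known. At stake is a misread signal from a pilot of a cream that section 10.3 says is untested in humans. Apparent slow healing could be taken as harm, or apparent fast healing as benefit, when either may only reflect who is left in the comparison.

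**Working it through.** **Inputs from the documents.** Rates of 65% and 20%, 2:1 allocation, and 30 and 15 evaluable patients (sections 5.2 and 8.2). The planning statement is "Sample size calculation was determined using significance/alpha (α) of 0.05", "to at least detect a difference in incidence of 45% and power (β) of 80" (per cent).

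**1. The plan's own sample size.** Two proportions, two-sided, no continuity correction, 2:1. The pooled rate is (0.65 + 2 × 0.20)/3 = 0.35.

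n(control) = [1.96 × √(0.35 × 0.65 × 1.5) + 0.8416 × √(0.65 × 0.35 + 0.20 × 0.80/2)]² / 0.45² = (1.145 + 0.467)² / 0.2025 = 12.8, so 13.

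Total = 13 + 26 = 39, which matches the plan. The two rates are therefore the working basis of the design.

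**2. Size of the healing subset.**
- Dermaprazole: 30 × 0.20 = 6 (binomial 95% range 2 to 11).
- Aquaphor: 15 × 0.65 = 9.75 (range 6 to 13).
- Together about 16 of 45 patients.

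**3. Three ways to get from 65% to 20%.** The documents give no healing times, so these are assumed. On Aquaphor, 35% of patients never reach grade 2, 45% heal in 14 days and 20% heal in 35 days. Among Aquaphor cases the mean is (0.45 × 14 + 0.20 × 35)/0.65 = 13.3/0.65 = 20.5 days. Over all Aquaphor patients it is 13.3 days. On Dermaprazole:
- Only 14-day cases prevented: cases 35.0 days; all patients 0.20 × 35 = 7.0.
- Even prevention: cases 20.5 days; all patients 0.20 × 20.46 = 4.1.
- Severity shifted down (the 14-day group becomes none, the 35-day group becomes 14-day): cases 14.0 days; all patients 0.20 × 14 = 2.8.

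| Mechanism | Mean days among cases, Aquaphor v Dermaprazole | The cream looks | Mean grade 2+ days, all patients |
|---|---|---|---|
| Prevents milder cases only | 20.5 v 35.0 | 14.5 days slower | 13.3 v 7.0 |
| Prevents evenly | 20.5 v 20.5 | no different | 13.3 v 4.1 |
| Shifts severity down | 20.5 v 14.0 | 6.5 days faster | 13.3 v 2.8 |

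In the first row no patient is worse off on the cream.

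**4. Simulated 30:15 trials** (same mix, assumed SDs of 5 and 8 days, t-test among cases):
- Milder cases only: the cream looks slower in 99.6% of trials, significantly so in 66%. A Wilcoxon test on all patients is significant in the cream's favour in 65%.
- Less extreme selection: with 5% mild and 15% severe cases left on the cream, it looks slower in 93% of trials, by about 9 days. With 8% and 12%, 83% and about 6 days.
- Even prevention: the cream looks slower in about 50%, significantly so in about 3%. The all-patient test detects benefit in 84%.
- Severity shift: the cream looks slower in about 6%, significantly so in 0.1%.

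**5. A second model, without the two-group mix.** Susceptibility is continuous and correlated with healing time (assumed median 21 days, log-SD 0.5).
- Cream prevents grade 2+ at the planned rates and has no effect on healing: median among cases, Aquaphor v Dermaprazole, is 22.9 v 26.0 days at correlation 0.3, 24.1 v 29.8 at 0.5 and 25.4 v 34.1 at 0.7.
- Healing follows a severity that the cream has lowered: at correlation 0.5 the medians are 24.1 v 21.9, in the cream's favour.

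Both models show the same thing: the sign depends on the mechanism.

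**The case against.** **The plan does not name this test.** Item 2.2.2.3 says assess, not compare, and the t-test comes from a general sentence in section 8.3 that never mentions healing. This stands. A reader might infer that the protocol prescribes a t-test on healing time; it does so only by default. But no other between-arm method is given, so that default is what an analyst would follow.

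**The endpoint is exploratory.** This also stands, and section 8.3 puts safety and tolerability ahead of comparative results. It lowers the status of the result but does not make it interpretable.

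**The cream may well lower severity in everyone.** Section 3.2 describes an anti-inflammatory agent with wound closure in most treated animals, so a downward shift is at least as plausible as preventing every mild case and no severe one. This stands, and it rules out any claim about a known direction of bias.

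**Equal healing among cases under even prevention is not an error.** It is a correct statement about those cases. The prevention benefit is carried by the primary endpoint and by items 2.2.2.1 and 2.2.2.2.

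**An all-patient measure answers a different question.** Under even prevention it differs (13.3 v 4.1) only because incidence differs. This stands too, and the replacement must be labelled accordingly.

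**Conclusion.** The point holds as one of interpretation. On the plan's rates, a between-arm test of healing time would compare about 6 with about 10 patients selected by an event that treatment is expected to change, and nothing in the documents corrects for this. The result is not a treatment effect on healing.

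A reader might go further and infer that an effective cream will look slower to heal, or that the secondary conclusion must be wrong whatever happens. The documents do not support either. They give no healing times, no severity split and no mechanism, and the assumed cases run from 14.5 days slower, through no difference, to 6.5 days faster. The simulated 99.6% and 66% describe a near-worst case, not this trial.

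Nor does the point touch the primary comparison of grade 2+ rates or the sample size of 39, which reproduces. It is worth correcting because the remedy is cheap, not because the trial's main conclusion is at risk.

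**What to change.** **Healing time.** In 2.2.2.3 and 8.3, define healing and report time to healing among patients who reached grade 2+ descriptively by arm, with no between-arm test.

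**Between-arm comparison.** Add days at grade 2+ from the start of radiation to the Month 3 visit, counting 0 for patients who never reach grade 2. Use all randomised patients with follow-up data and say how this set relates to the completers in 8.4. Compare with a Wilcoxon test and a difference in means with bootstrap confidence interval. State whose grades are used, since section 2.1.1 collects both the radiation oncologist's and the blinded dermatologist's. Month 3 is already the time at which section 8.1 evaluates all endpoints.

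**Rules to set in advance.**
- The calendar schedules no skin exam, photograph or dermatitis grade in Weeks 8 and 9; the next is Month 1, at 30 ± 14 days after radiation. Set an interpolation rule, for example the midpoint between the last grade 2+ and the first lower grade, with the earliest and latest possible dates as sensitivity analyses.
- State what is counted after death or drop-out. Simply stopping the count would credit early leavers with fewer days.

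**Cost.** Text changes and analysis rules only, with no new visits. Much of the post-radiation duration will be interpolated. The measure blends occurrence with duration and partly overlaps the primary endpoint, so label it grade 2+ burden, not healing speed.

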3.1 Study Disease

Radiation dermatitis is an expected complication of radiotherapy that can lead to worse patient-reported quality of life during treatment and worse cosmesis, particularly in obese patients. Patients within the Bexar County Health System are more likely to have risk factors associated with radiation dermatitis, including obesity and diabetes. While our mostly low socioeconomic status patients stand to benefit the most from upfront therapy in order to prevent later cancer-related morbidity and mortality, they are also more likely to suffer from acute treatment-related morbidity, including radiation dermatitis.

Given the unmet medical need for therapies to address radiation dermatitis, our basic science team has been investigating candidate drugs to mitigate the problem. After screening a library of 130,000 compounds, we found that proton pump inhibitor (PPIs) have previously unrecognized yet potent effect in modulating inflammation and fibrosis induced by chemotherapy and ionizing radiation. Radiation-induced dermatitis occurs in most patients following radiotherapy. According to the NCI-CTCAE (Services, 2017) and RTOG (J. D. Cox, 1995) scoring systems, mild dermatitis (Grade I) is characterized by mild redness (erythema), epidermal thickening (hyperkeratosis) or dry desquamation and appears shortly after initiation of T. Moderate dermatitis (Grade II) occurs within two weeks of radiotherapy and manifests painful and intense erythema, loss of hair from the root (epilation), blisters and edema. Of note, the presence of grade II toxicity is generally regarded as clinically significant toxicity. In severe dermatitis (Grade III and IV), moist desquamation occurs excessively and may lead to persistent inflammation, full-thickness skin necrosis and severely painful ulceration that is prone to infection. The acute effects occur almost immediately at radiation doses between 2 and 40 Gray (2-40 Gy) whereas chronic effects occur several months-to-years after exposure to high radiation doses (> 45 Gy) and typical skin changes include atrophy, scarring and spider veins (telangiectasia) (S. R. Hymes, 2006).

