5.3 Radiotherapy Administration

Dose, Prescription, and Planning: Head and neck radiation of over 60Gy will be permitted with or without boost up to 70Gy (but not higher). Radiation is to be delivered 5 days per week (with exception of weeks with holidays), using intensity-modulated technique.

Simulation and Treatment: CT-based simulation with thermoplastic mask and volumetric planning must precede treatment. Tissue-equivalent bolus is permitted on protocol. Daily cone beam CT images are required to confirm accurate delivery.

Resimulation: Will be done in the last week of radiotherapy to allow for recalculation of beams.

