9 DATA MANAGEMENT

Patient information will be acquired from patient medical records within the clinical site Electronic Medical Record (EMR) system.

Page 16 of 23

Patient characteristics including age, race/ethnicity, initial biopsy result, cancer stage, BMI and known comorbidities will be collected.

Patient data for analysis will be captured using REDCap. Paper forms including the skindex16 questionnaires will be kept in a locked cabinet in the Radiation Oncology offices and input into REDCap. Photos of patients' skin reaction will also be kept on this limited-access network drive. Patient information will be de-identified for final statistical analysis by removal of patient names and MRNs. Each patient will be assigned a study code at time of study registration.

Information gathered from the planning system will include the V20 to V80 in 5 Gy increments reaching skin shell contours of "skin minus 3 millimeters" and "skin minus 5 millimeters" as well as the total dose. This will be collected for both simulation scans.

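### The skin-dose grid has no level below 20 Gy, although the plan seeks the dose at which dermatitis of any grade appears and puts acute effects from 2 Gy

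*Combined protocol and SAP*

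**What the plan says.** Under 2.1.2 Secondary Objectives, item 2.2.2.5 reads "To evaluate the threshold dose at which RD appears in either arm". The tool for this is given as "utilizing skin dose tracking structures (V20 to V80 in 5 Gy increments reaching skin shell contours of" two depths, 3 mm and 5 mm below the skin surface. Item 2.2.2.6 applies the same metrics to a new simulation scan in the last week of radiotherapy. Neither item names a grade of RD.

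Section 8.3 turns the grid into an analysis: "We will also evaluate the incidence of RD for specific radiation skin dose stratification by reviewing the V20 to V80 in 5 Gy increments". It adds: "This will be done on both the original dosimetry as well as a recalculated plan from the resimulation scan". Section 9 lists what is taken from the planning system, again "V20 to V80 in 5 Gy increments reaching skin shell contours of" the same two depths, together with total dose. No section mentions a level below V20.

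The background in section 3.1 states: "The acute effects occur almost immediately at radiation doses between 2 and 40 Gray". It says that grade I appears soon after treatment starts. For grade II it gives a time but no dose: "Moderate dermatitis (Grade II) occurs within two weeks of radiotherapy".

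Section 5.3 allows courses of more than 60 Gy, "with or without boost up to 70Gy (but not higher". This is a limit on the prescribed dose.

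**The concern.** A search for a threshold should cover the doses at which the investigators themselves expect the event to start. The plan's background puts that range at 2 to 40 Gy, and the grid begins at 20 Gy. Because the objectives count RD of any grade, early and mild reactions are in scope, and these are the ones most likely to start at low dose.

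Two of the seven secondary objectives rest on this grid, and so does the dose-stratified incidence in section 8.3. Patients also undergo a resimulation in the last week, partly so that RD can be correlated with updated dosimetry. If the low-dose part of the skin shell is never exported, that scan yields less than it could.

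**Working it through.** **Inputs.** Grid V20 to V80 in steps of 5 Gy (2.1.2, 8.3, 9). Acute range 2 to 40 Gy (3.1). Two shells and two scans (8.3, 9). Prescription above 60 and up to 70 Gy, 5 treatments a week (5.3). The documents give no derivation for the grid and no dose per fraction.

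**Step 1: the grid as written.** Number of levels = (80 − 20)/5 + 1 = 13. Values per patient = 13 × 2 shells × 2 scans = 52.

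**Step 2: overlap with the stated acute range.** The range is 40 − 2 = 38 Gy wide. Levels inside it are 20, 25, 30, 35 and 40, so five. The part below the lowest level is 20 − 2 = 18 Gy, and 18/38 = 47%. The part covered is 20/38 = 53%. These are shares of width only; they do not say how likely a threshold is in each part.

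**Step 3: does the gap depend on how the metric is read?** Vx is the amount of the shell receiving at least x Gy.
- If skin dose is accumulated to the day RD appears, which the opening summary's remark about tracking skin dose might suggest, onset before 20 Gy can only be recorded as under 20 Gy.
- If Vx is taken from the whole plan, as section 8.3 describes, skin receiving less than 20 Gy forms one undivided remainder, and incidence cannot be split within it.

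The gap is present either way.

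**Step 4: could onset plausibly fall in the gap?** This step is illustrative, because the fraction size is an assumption. Dose after two weeks = 10 × total dose/(5 × weeks), with courses of 6 or 7 weeks assumed.

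| Total dose | Weeks | Gy per fraction | After 10 fractions |
|---|---|---|---|
| 60 Gy | 7 | 1.71 | 17.1 Gy |
| 60 Gy | 6 | 2.00 | 20.0 Gy |
| 70 Gy | 7 | 2.00 | 20.0 Gy |
| 70 Gy | 6 | 2.33 | 23.3 Gy |

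These are prescribed doses. If the shell receives 50% to 100% of prescription (assumed), then at 2 Gy per fraction the skin has had 10 to 20 Gy after two weeks. Early reactions could therefore fall below the first level. This shows that the gap matters; it does not locate any threshold.

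**Step 5: the upper end.** Two of the 13 levels, 75 and 80, exceed 70 Gy. At a 70 Gy prescription, V75 is non-zero if the shell contains a hot spot of 75/70 = 107.1%, and V80 if it contains one of 80/70 = 114.3%. Assumed hot spots of 107%, 110% and 115% give 74.9, 77.0 and 80.5 Gy. The documents set no limit on local maximum dose, so these levels cannot be called empty in advance.

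**Step 6: the grid extended downward.** V5 to V80 gives (80 − 5)/5 + 1 = 16 levels. Coverage of the acute range becomes (40 − 5)/38 = 35/38 = 92%. Values per patient become 16 × 2 × 2 = 64, which is 12 more.

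**The case against.** The strongest reply is that the metric and the background sentence describe different things. Section 8.3 relates RD incidence to values from a complete plan, so V20 is not a moment in treatment, and a dose reached by week 2 says little about where the grid should start. The larger gap may be that no rule links Vx to the first appearance of RD, and that weekly grading (about 10 Gy prescribed per week at an assumed 2 Gy per fraction) is coarser than a 5 Gy step. That stands as a separate matter, and a wider grid would not settle it. Equally, settling it would not supply dose levels that were never exported.

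Three stronger readings are tempting, and the documents do not support them.

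- A reader might infer that grade 2 has already begun at 20 Gy. Section 3.1 gives no dose for grade II. The inference needs an assumed fraction size, two weeks counted from the start of treatment, and skin dose equal to prescribed dose. Section 8.2 also expects grade 2 or higher in only about 65% of controls and 20% of the Dermaprazole arm, so 35% and 80% would never reach it. Those rates do not answer the narrower point, which concerns RD of any grade in those who develop it.
- A reader might infer that the grid cannot bracket a threshold at all. Five levels lie between 20 and 40 Gy, so a threshold there can be bracketed.
- A reader might infer that V75 and V80 are a defect. Levels above the highest dose present do no harm, and hot spots may reach these two.

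It can also be said that section 9 does not forbid lower levels, and that they might be retrieved later. The documents do not provide for either.

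**Conclusion.** The point holds in a narrow form. As written, the plan cannot locate an RD threshold below 20 Gy or stratify RD incidence there, although its own background puts acute effects from 2 Gy. The uncovered part is 18 of 38 Gy (47%) of that range; 20 to 40 Gy is adequately stepped. This rests on two readings of the text: that RD in 2.2.2.5 and 2.2.2.6 means any grade, since none is named, and that the range in section 3.1 reflects what the investigators expect. It does not depend on fraction size, on the ratio of skin dose to prescription, or on hot spots.

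The severity is minor. Section 8.3 treats everything outside the primary endpoint as exploratory, and neither the primary comparison nor the safety rules use this grid.

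**What to change.** In objective 2.2.2.5 (and so 2.2.2.6), section 8.3 and section 9, change the lower end of the grid so that it reads V5 to V80 in 5 Gy steps. Alternatively, state that the full dose-volume histogram of both shells will be exported from both scans. Keep V75 and V80, and leave the analysis free to use all levels; the documents give no ground for making the low levels the main range.

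The cost is three more exported values per shell per scan (12 per patient) and a larger number of exploratory comparisons, which the report should acknowledge. The values come from plans that the protocol already requires, so no scan, visit or treatment changes.
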